6.10. Additional Analysis

The following additional analyses will be performed on primary continuous endpoints of both part A and part B.

“Retrieved dropout” analysis

Part A

The primary analysis and sensitivity analyses of the primary endpoint only utilize the active joint count data observed before treatment failure visit or subjects discontinued the study treatment. In this study, subjects who were considered as treatment failures or discontinued the study treatment were encouraged to stay in the study and complete the assessments. [REDACTED]

[REDACTED]

[REDACTED] The change in joint count score will be computed based on all active joint count scores collected, and the same MMRM model as for the primary analysis.

The “retrieved dropout” analysis addresses a different estimand (effectiveness estimand) than the primary and sensitivity analyses (efficacy estimand) of the primary endpoint, by using joint count scores collected after cessation of study treatment, including while being treated with other therapies. Therefore, results of this analysis will not be considered as a sensitivity analysis of the primary endpoint but as an additional analysis addressing a complementary question.

CONFIDENTIAL

The information contained herein may not be used, disclosed, or published without the written consent of Biogen MA Inc.

To examine the pattern of missing data, the number and percentage of subjects with an active joint count score at each treatment week will be presented by treatment group for both the observed on-treatment data and the retrieved dropout data.

Part B

The primary analysis and sensitivity analyses of the primary endpoint only utilize the CLASI-A score observed before treatment failure visit or subjects discontinued the study treatment. In this study, subjects who were considered as treatment failures or discontinued the study treatment were encouraged to stay in the study and complete the assessments. [REDACTED]

[REDACTED] The change in CLASI-A score will be computed based on all CLASI-A score scores collected, and the same MMRM model as for the primary analysis.

The “retrieved dropout” analysis addresses a different estimand (effectiveness estimand) than the primary and sensitivity analyses (efficacy estimand) of the primary endpoint, by using CLASI-A scores collected after cessation of study treatment, including while being treated with other therapies. Therefore, results of this analysis will not be considered as a sensitivity analysis of the primary endpoint but as an additional analysis addressing a complementary question.

To examine the pattern of missing data, the number and percentage of subjects with an active joint count score at each treatment week will be presented by treatment group for both the observed on-treatment data and the retrieved dropout data.

CONFIDENTIAL

The information contained herein may not be used, disclosed, or published without the written consent of Biogen MA Inc.

7. SAFETY ANALYSES

7.1. General Considerations

All safety analyses will be performed for the safety population. No statistical testing will be performed on the safety data.

7.2. Analysis of Adverse Events (AEs)

All AEs will be coded by system organ class and preferred term using the MedDRA dictionary (Version 21.1 or the most updated version at data base lock). In this study, only treatment emergent AEs (i.e. those that occurred or worsened after the first randomized dose through the end of study) will be analyzed. Such AEs will have an onset date on or after the date of first randomized dose or will have presented prior to the first randomized dose and subsequently worsened. Therefore, whenever an analysis of summary of AEs is mentioned, it is intended that this is in reference to treatment-emergent AEs.

The number and percentage of subjects experiencing one or more treatment-emergent AEs in the following categories will be summarized.

- Any AE
- Any mild AE
- Any moderate AE
- Any severe AE
- Any related AE
- Any serious AE
- Any related serious AE
- Any AE that led to withdrawal of study drug
- Any AE that led to study withdrawal
- Any AE that led to drug interrupted, dose not changed
- Deaths

CONFIDENTIAL

The information contained herein may not be used, disclosed, or published without the written consent of Biogen MA Inc.

 Biogen	Statistical Analysis Plan 230LE201	<V 2.0>
--	---	----------------------

The following summaries will be presented.

- AEs by system organ class (SOC) and preferred term (PT)
- AEs by PT
- AEs by PT with an incidence of 5% or more in any of the treatment groups
- AEs by PT with at least 2% higher in incidence for either BIIB059 group compared to placebo
- Serious AEs by SOC and PT
- Treatment-related serious AEs by SOC and PT
- Severe AEs by SOC and PT
- AEs by relationship to study treatment by SOC and PT
- Treatment-related AEs by SOC and PT
- AEs that led to discontinuation of study drug by SOC and PT
- AEs that led to withdrawal from study by SOC and PT
- AEs by maximum severity by SOC and PT
- Suspected unexpected serious adverse reactions (SUSAR) by SOC and PT

To count the number of subjects who experience each AE, a subject experiencing the same AE multiple times will only be counted once for that preferred term. Similarly, if a subject experiences multiple AEs within the same system organ class, that subject will be counted only once for that system. For subjects experiencing the same AE more than once, the occurrence of the AE with the greatest severity will be used in the calculation of incidence by severity.

The following listings will be presented.

- Listing of serious AEs
- Listing of AEs that led to discontinuation of study drug
- Listing of AEs that led to withdrawal from study
- Listing of all AEs

CONFIDENTIAL

The information contained herein may not be used, disclosed, or published without the written consent of Biogen MA Inc.

7.3. Analysis of Laboratory Tests

7.3.1. Shift Analysis for Lab Tests

Laboratory abnormalities will be summarized with shift from baseline tables. Each hematology and chemistry value will be flagged as “low”, “normal”, or “high” relative to the normal ranges of the laboratory that performed the assay, or as “unknown” if no results are available. Each urinalysis value will be flagged as “positive”, “negative”, or “unknown” if no values are available.

Shift from baseline to high/low status for hematology and chemistry parameters and shifts from baseline to high/positive for urinalysis will be presented. In each summary, the denominator for the percentage is the number of patients at risk for the shift. The number at risk for a shift to low is the number of subjects whose baseline value was not low and who had at least one post-baseline value. The number at risk for a shift to high is the number of subjects whose baseline value was not high and who had at least one post-baseline value. Subjects will be counted only once for each parameter and each type of shift regardless of how many post-dosing assessments had that type of shift. A shift to high includes normal to high, low to high, and unknown to high; a shift to low includes normal to low, high to low, and unknown to low. A shift to positive includes ‘negative’ to ‘positive’ and ‘unknown’ to ‘positive’.

A listing of normal ranges will be provided for all laboratory parameters.

7.3.2. Analysis of Change from Baseline and Actual Values

The absolute and percent changes from baseline by visit will be summarized for quantitative laboratory parameters using descriptive statistics. Actual values will also be summarized in a similar way.

7.3.3. Analysis of Potentially Clinically Significant Abnormalities

The number and percentage of subjects with potentially clinically significant abnormal values for laboratory parameters will be summarized. A listing of potentially clinically significant abnormal

CONFIDENTIAL

The information contained herein may not be used, disclosed, or published without the written consent of Biogen MA Inc.

values will also be presented. Potential clinical significance will be determined for selected parameters based on the criteria listed below.

Parameter Name	PCS Low	PCS High
Hematology		
White Blood Cells	$<3.0 \times 10^3/\text{mm}^3$	$>16 \times 10^3/\text{mm}^3$
Neutrophils	$<1.5 \text{ k/mm}^3$	$>13.5 \text{ k/mm}^3$
Lymphocytes	$<0.8 \text{ k/mm}^3$	$>12 \text{ k/mm}^3$
Monocytes	N/A	$>2.5\text{k/mm}^3$
Eosinophils	N/A	$>1.6 \text{ k/mm}^3$
Basophils	N/A	$>1.6 \text{ k/mm}^3$
Hemoglobin		
for Females	$\leq 9.5 \text{ g/dL}$	$\geq 17.5 \text{ g/dL}$
For Males	$\leq 11.5 \text{ g/dL}$	$\geq 19.0 \text{ g/dL}$
Hematocrit		
for Females	$\leq 32\%$	$\geq 54\%$
for Males	$<37\%$	$\geq 60\%$
Red Blood Cells (RBC)	$\leq 3.5 \times 10^6/\text{mm}^3$	$\geq 6.4 \times 10^6/\text{mm}^3$
Platelet count	$\leq 75 \times 10^3/\text{mm}^3$	$\geq 700 \times 10^3/\text{mm}^3$
Chemistry		
Sodium	$\leq 126 \text{ mEq/L}$	$\geq 156 \text{ mEq/L}$
Potassium	$\leq 3.0 \text{ mEq/L}$	$\geq 6 \text{ mEq/L}$
Chloride	$\leq 90 \text{ mEq/L}$	$\geq 118 \text{ mEq/L}$
Bicarbonate	$\leq 16 \text{ mEq/L}$	$\geq 35 \text{ mEq/L}$
Calcium	$<8.0 \text{ mg/dL}$	$\geq 12 \text{ mg/dL}$
Magnesium	$<1.2 \text{ mEq/L}$	$>2.3 \text{ mEq/L}$
Inorganic Phosphorous	$\leq 1.7 \text{ mg/dL}$	$\geq 5.3 \text{ mg/dL}$
Aspartate aminotransferase (AST)	N/A	$\geq 3 \text{ xULN}$
Alanine Aminotransferase (ALT)	N/A	$\geq 3 \text{ x ULN}$
Alkaline phosphatase	N/A	$\geq 3 \text{ x ULN}$

CONFIDENTIAL

The information contained herein may not be used, disclosed, or published without the written consent of Biogen MA Inc.

Creatinine	N/A	>1.5xULN
Total Bilirubin	N/A	>1.5xULN
Total Protein	≤ 4.5 g/dL	≥ 10 g/dL
Albumin	≤ 2.5 g/dL	N/A
Uric Acid for Females for Males	N/ A	≥ 8.5 mg/dL ≥ 10.5 mg/dL
Glucose (Fasting) (Non-fasting)	≤ 40 mg/dL ≤ 40 mg/dL	≥ 160 mg/dL ≥ 250
Creatinine Phosphokinase (CPK)	N/A	>3x ULN
Total Cholesterol	N/A	>300 mg/dL

CONFIDENTIAL

The information contained herein may not be used, disclosed, or published without the written consent of Biogen MA Inc.

7.4. Vital Signs

The number and percentage of subjects with clinically relevant abnormalities in vital signs post-baseline will be summarized. Subjects evaluated will be safety subjects with a baseline and at least one post-baseline assessment for that vital sign. Abnormal vital signs will be determined by the following criteria.

Vital Sign	Criteria to determine clinically relevant abnormal vital signs
Temperature	>38°C and an increase from pre-dose of at least 1°C
Pulse	>100 beat per minute (bpm) and an increase from baseline of more than 20 bpm, or <50 bpm and a decrease from baseline of more than 20 bpm.
Systolic Blood Pressure	>160 mmHg and an increase from baseline of more than 40 mmHg, or <90 mmHg and a decrease from baseline of more than 30 mmHg
Diastolic Blood Pressure	>100 mmHg and an increase from pre-dose of more than 30 mmHg, or <45 mmHg and a decrease from pre-dose of more than 20 mmHg

A listing of all vital sign values will be presented for subjects with any vital signs abnormalities. Clinically relevant abnormal vital signs will be flagged in the listing.

7.5. ECG

The number and percentage of subjects with shifts from normal at baseline to abnormal in ECG results will be summarized. If there is no ECG result at baseline, the subject will be counted in the unknown category. A shift to abnormal will include a shift from “unknown” or “normal” at baseline to “abnormal” post- baseline.

7.6. Physical Examination

Abnormal findings which are noted after subjects received study treatment and are deemed by the investigator as clinically significant will be reported as AEs and included in AE analyses.

CONFIDENTIAL

The information contained herein may not be used, disclosed, or published without the written consent of Biogen MA Inc.

8. PK ANALYSES

For the PK population, serum concentration of BIIB059 will be summarized descriptively using nominal time points. The mean values (+/- SD) will be plotted over time by treatment group on the linear and log linear scale. Measurements that are below the level of quantification (BLQ) will be set to missing before statistics are calculated, if the BLQ occurs before the first measurable concentration (such as predose), it should be set to zero. If the value of the concentration is "Non-Determinable", then the concentration value will be set to missing.

Additionally, a population PK analysis will be conducted to characterize the PK of BIIB059 in subjects with SLE and CLE, estimate population PK parameters of BIIB059, estimate random inter- and intrasubject variability, and estimate random residual variability associated with the estimation of PK model parameters. The PK parameters calculations are detailed in a separate PK analysis plan. PK parameters will be summarized with the following statistics: n, mean, SD, percent coefficient of variation, median, minimum, maximum, and geometric mean.

The population PK analysis may also be used to identify sources of variability (continuous and categorical covariates) that may influence the PK of BIIB059 in patients. In addition, exposure-response (efficacy) analysis may be performed to evaluate the relationship between exposure of BIIB059 and clinical endpoints, which will be used to justify doses for Phase 3 studies. Further details can be found in the PK analysis plan.

9. OTHER ANALYSES

The quantitative or qualitative analysis of the relationship between the BIIB059 exposure and the primary and secondary endpoints will be performed. As described in [Section 8](#), details of the analysis will be included in a separate PK analysis plan for the PKPD modeling.

CONFIDENTIAL

The information contained herein may not be used, disclosed, or published without the written consent of Biogen MA Inc.

9.1. Immunogenicity Data

The analysis population for immunogenicity is defined as all subjects who are randomized and who have been dosed with study treatment and have at least 1 post-dose immunogenicity sample collected.

Summary of positive anti-BIIB059 serum antibodies will be presented by visits and by treatment group.

To define immunogenicity status the following rules will be used

- The baseline value is defined as the latest immunogenicity data collected at any time prior to the first dose. If no immunogenicity data are collected prior to the first dose, the baseline value is missing and will be imputed as anti-drug antibody negative for immunogenicity analyses.
- Subjects with at least one confirmed post-treatment positive result will be considered positive for anti-BIIB059 antibodies if their baseline result is negative.
- Subjects where none of the post-treatment samples were positive for anti-BIIB059 antibodies will be considered negative regardless of their baseline result.
- For subjects that are confirmed positive at baseline and have at least one post-treatment sample with a ≥ 4 -fold increase in titer will be considered positive for anti-BIIB059 antibodies. Subjects that are positive at baseline, with subsequent post-treatment samples titers that are within 2-fold will be considered negative for anti-BIIB059 antibodies.
- In addition, for subjects that are considered anti-BIIB059 antibody positive with final immunogenicity data, the following may be evaluated:
 - Persistence of the anti-BIIB059 antibody response: More than one positive evaluation that are ≥ 112 days apart or a positive evaluation at the last time point with no further samples available.
 - Transient anti-BIIB059 antibody response: A single positive evaluation or more than one positive evaluation <112 days apart.

The impact of anti-BIIB059 antibodies on PK parameters may be evaluated by considering antibody status (positive or negative, persistent/transient) as a co-variate in the analysis. The impact on efficacy may be evaluated by summarizing key efficacy endpoints by antibody status (positive or negative, persistent/transient). In addition, to determine the relationship (if any) of

CONFIDENTIAL

The information contained herein may not be used, disclosed, or published without the written consent of Biogen MA Inc.

anti-BIIB059 antibodies on safety, incidence of adverse events, serious adverse events and events of particular interest will be presented by antibody status (positive or negative, persistent/transient) as well as by timing of the events.

CONFIDENTIAL

The information contained herein may not be used, disclosed, or published without the written consent of Biogen MA Inc.

10. INTERIM ANALYSES

10.1. Interim Analysis 1 (IA1): Futility

An unblinded interim analysis for futility Part B (and possible expansion of Part A) will be performed. The IA will be performed after approximately 45% of the subjects in Part B (PV2 and subsequent version) have completed their Week 12 Treatment Visit.

At the time of the IA, it is estimated that approximately 50% of subjects in Part A will have completed their Week 12 treatment visit. Depending on the outcome of the IA, BIIB059 doses may be adjusted (downwards or upwards), with predicted exposures within what was shown to be safe and well tolerated. In addition, up to 70 subjects may further be enrolled into Part A, which objectives are as follow:

- 1) potentially include an expanded SLE patient population based on more inclusive criteria,
- 2) potentially adjust the dose of BIIB059 and,
- 3) To provide greater precision for the Week 24 endpoints, including the SRI-4.

Unblinded subject baseline characteristics (e.g., Joint Count, SLEDAI-2K) will be assessed. The randomization stratification factors will be re-evaluated in the expanded enrollment to achieve balance between treatment groups.

The IA will be performed by independent personnel (internal and/or external) not involved in the conduct of the study. Unblinded tables, listings, or graphs (TLGs) will be generated by independent personnel (internal or external) not involved in the conduct of the study.

The team that performs the unblinded interim analysis must not be involved in the study conduct between the interim DBL and the final DBL. They can however be part of the final analysis team after the final DBL has occurred. At the discretion of Biogen, unblinded TLGs and/or data may be shared with Sponsor personnel who are not directly involved in the conduct of the study.

Additional information will be provided in an unblinding plan.

The endpoints and analysis to be included in the IA1 are listed in [Appendix B](#).

CONFIDENTIAL

The information contained herein may not be used, disclosed, or published without the written consent of Biogen MA Inc.

10.2. Interim Analysis 2 (IA2): End of Treatment Periods

After the last subjects complete the Double-Blind Treatment Periods for Part A (at Week 24) and Part B (at Week 16), an interim database lock will occur and an IA of efficacy and safety data will be conducted. All Investigators, study site personnel, and subjects will remain blinded to treatment assignments until after the end of the study. Members of the Biogen study team not in direct contact with the study sites will have access to the study data after all subjects complete all Week 24 assessments in Part A and all Week 16 assessments in Part B. Members of the Biogen study team who become unblinded to the data for this IA will have no further contact with study sites until after the final database lock.

Unblinding details will be provided in the unblinding plan.

The endpoints and analysis to be included in the IA1 and IA2 are listed in [Appendix B](#).

11. SAMPLE SIZE JUSTIFICATION

Part A:

The sample size for Part A is 100 subjects, randomized in a 1:1 ratio, with 50 subjects allocated to each treatment group. This sample size will provide approximately 71% power to detect a statistically significant difference in the Week 24 absolute change from baseline active joint count, assuming a standard deviation of 6, a maximal difference of BIIB059 over placebo of 2.5, a 20% dropout rate, and a 2-sided testing at the 0.02 level significance. If the study is not stopped for futility at the IA, then up to an additional 70 subjects may be enrolled into Part A. These may increase the power to approximately 87% at Week 24.

Part B:

The planned sample size for Part B is 100 subjects, randomized in a 1:1:1:1 ratio, with 25 subjects per dosage arm of BIIB059 (50 mg, 150 mg, and 450 mg) and placebo. This sample size will provide approximately 90% power to detect a dose-response relationship in the Week 16 percent change from baseline score in CLASI-A score, assuming a standard deviation of 30, a maximal difference of BIIB059 over placebo of 27.5%, and a 20% dropout rate. Five different

CONFIDENTIAL

The information contained herein may not be used, disclosed, or published without the written consent of Biogen MA Inc.

dose-response relationships will be tested at the 2-sided 10% significance level with the MCP-Mod method being used to control for multiplicity. Further details about the dose-response analyses can be found in [Section 6.2](#).

The power calculations are based on assuming a standard deviation of 30, a maximal difference of BIIB059 over placebo of 27.5% at 450 mg, and a 20% dropout rate.

CONFIDENTIAL

The information contained herein may not be used, disclosed, or published without the written consent of Biogen MA Inc.

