16.8. Sample Size Considerations

Part A:

The sample size for Part A is 100 subjects, randomized in a 1:1 ratio, with 50 subjects allocated to each treatment group. This sample size will provide approximately 71% power to detect a statistically significant difference in the Week 24 absolute change from baseline active joint count, assuming a standard deviation of 6, a maximal difference of BIIB059 over placebo of 2.5, a 20% dropout rate, and a 2-sided testing at the 0.2 level significance. Additional information will be provided in the Statistical Analysis Plan (SAP). If the study is not stopped for futility at the IA (details in Section 16.7), then up to 70 additional subjects may be added to Part A. If an additional 70 subjects are added, the power will increase to approximately 87% at Week 24.

Part B:

The planned sample size for Part B is 100 subjects, randomized in a 1:1:1:1 ratio, with 25 subjects per dosage arm of BIIB059 (50 mg, 150 mg, and 450 mg) and placebo. This sample size will provide approximately 90% power to detect a dose-response relationship in the Week 16 percent change from baseline score in CLASI-A score, assuming a standard deviation of 30, a maximal difference of BIIB059 over placebo of 27.5%, and a 20% dropout rate. Five different dose-response relationships will be tested at the 2-sided 10% significance level with the MCP-Mod method being used to control for multiplicity [Bretz 2005].

CONFIDENTIAL

The information contained herein may not be used, disclosed, or published without the written consent of
Biogen MA Inc.

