6. EFFICACY ANALYSES

6.1. General Considerations

For both Part A and Part B, the efficacy analyses will be performed using the MITT population and will be considered as the primary analyses. For each endpoint, additional conditions may apply for pooling of data across protocol versions (see [Section 3.1](#)). The final model for each analysis in the MITT population will also be used for the PP analysis. A complete list of all the planned analyses and target population for the primary and secondary endpoints is provided in [Appendix A1](#) (Part A) and [Appendix A2](#) (Part B).

Unless otherwise specified, statistical testing across all efficacy endpoint will be performed to compare each BIIB059 dose (Part A: 450 mg; Part B: 50, 150 or 450 mg) with placebo at the 2-sided, 0.05 significance level. P-values and corresponding 95% confidence intervals (CI) will be provided. P-values will be rounded to three decimal points before assessing statistical significance.

CONFIDENTIAL

The information contained herein may not be used, disclosed, or published without the written consent of Biogen MA Inc.

 Biogen	Statistical Analysis Plan 230LE201	<V 2.0>
--	---	----------------------

Summary statistics will be presented for all endpoints at all visits including follow-up visits. For continuous variables, the summary statistics will include number of subjects with data, mean, standard deviation (SD), median, first quartile (Q1), third quartile (Q3), minimum and maximum. For categorical endpoints, the summary statistics will generally include: number of subjects in the corresponding analysis population, number and percentage of subjects in each category.

Unless otherwise specified, week 2, 4, 8, 12, 16, 20 and, 24 will be included in all Part A “by visit” MMRM analyses.

Unless otherwise specified, week 2, 4, 8, 12 and, 16 will included in all Part B “by visit” MMRM analyses.

Additional study part specific efficacy analyses considerations are described in [Section 6.1.1](#) (Part A) and [Section 6.1.2](#) (Part B)

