6.5. Multiplicity Adjustment

Part A

There will be no adjustment for multiplicity at interim or final analysis for the primary or secondary endpoints in Part A.

Part B

Multiple Comparison Procedure-Modeling (MCP-Mod) methodology ([Bretz et al. 2005](#)) will be used to test the dose-response relationship across 3 doses of BIIB059 and PBO for the percent change from baseline in CLASI-A score at interim and final analysis. Five dose-response trends will be tested using the optimal contrasts as determined by the MCP-Mod methodology such that the overall Type I error rate is controlled at 0.05 (one-sided testing).

There will be no adjustment for multiplicity with secondary efficacy endpoints at interim or final analysis.

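### Part A's primary test is given three significance levels (0.2, 0.02, 0.05), and the stated 71% power is true only at 0.2, a level the visible SAP never states

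*SAP*

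**What the plan says.** Three places bear on the significance level for the Part A primary comparison, 450 mg against placebo on Week 24 change in active joint count.

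- **Protocol 16.8 (Sample Size Considerations).** 100 subjects, 50 per arm, SD 6, difference 2.5, "a 20% dropout rate, and a 2-sided testing at the 0.2 level significance". Power is given as about 71%, rising to about 87% if 70 subjects are added.
- **SAP 11 (Sample Size Justification).** The same sample size, SD, difference and dropout, and the same two powers ("This sample size will provide approximately 71% power to detect a statistically significant difference"; "These may increase the power to approximately 87% at Week 24"), but with "a 20% dropout rate, and a 2-sided testing at the 0.02 level significance".
- **SAP 6.1 (General Considerations).** "Unless otherwise specified, statistical testing across all efficacy endpoint will be performed to compare each BIIB059 dose" (the 450 mg arm is named for Part A) "with placebo at the 2-sided, 0.05 significance level", with 95% confidence intervals.

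The visible text of SAP 6.1.1 and 6.2.1, which set out the Part A model and primary analysis, gives no level. SAP 6.5 says of Part A only that "There will be no adjustment for multiplicity at interim or final analysis for the primary or secondary endpoints in Part A". The same section does give Part B its own level, one-sided 0.05, which agrees with the two-sided 10% in SAP 11.

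**The concern.** A single primary comparison needs one threshold, fixed in advance. Here the planning level differs between protocol and SAP by a factor of ten, and the level in the SAP's analysis section matches neither. The SAP also carries over the protocol's powers unchanged although it states a much stricter alpha, so at least one of its figures must be wrong.

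Two things are at stake. First, a Part A p-value between 0.02 and 0.2 (between 0.05 and 0.2 if 0.02 is a slip) can be called positive or negative depending on which section is cited. Second, anyone relying on 71% or 87% to judge what Part A can show, or whether to expand it, is relying on power at a level the SAP's default test does not use.

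Timing adds to this. Under SAP 10.2 and Appendix B, some sponsor staff see unblinded model-based Part A primary results at the second interim analysis. A level settled after that point could be thought to have been chosen to suit the result.

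**Working it through.** **Inputs** (identical in Protocol 16.8 and SAP 11 except for alpha)
- SD 6; difference 2.5; 1:1 allocation
- 100 subjects: 50 per arm × (1 − 0.20) = 40 evaluable per arm
- 170 subjects: 85 per arm × (1 − 0.20) = 68 evaluable per arm
- Two-sided alpha: 0.2 (Protocol 16.8), 0.02 (SAP 11), 0.05 (SAP 6.1)

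**Method.** Two-sample t-test with noncentral-t power:
- standard error = SD × √(2/n)
- noncentrality = difference / standard error
- degrees of freedom = 2n − 2

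For n = 40: standard error = 6 × √(2/40) = 1.342; noncentrality = 2.5/1.342 = 1.863; 78 df.
For n = 68: standard error = 6 × √(2/68) = 1.029; noncentrality = 2.5/1.029 = 2.430; 134 df.

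**Power** (normal approximation in brackets)

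| Two-sided alpha | Source | 100 subjects (40/arm evaluable) | 170 subjects (68/arm evaluable) |
|---|---|---|---|
| 0.2 | Protocol 16.8 | 0.717 (0.720) | 0.873 (0.875) |
| 0.05 | SAP 6.1 | 0.4525 (0.4615) | 0.674 (0.681) |
| 0.02 | SAP 11 | 0.310 (0.322) | 0.531 (0.541) |

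**Reproducing the plan's figures.** At 0.2 both stated powers, 71% and 87%, are reproduced. At 0.02 and 0.05 neither is. Ignoring dropout (50 per arm) does not rescue 71%: power is 54% at 0.05 and 39% at 0.02. Reading 0.02 as one-sided with 40 per arm gives 42%.

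**Threshold against planned effect** (40 per arm). The smallest difference reaching significance is critical t × 1.342:
- alpha 0.2: 1.292 × 1.342 = 1.73 joints
- alpha 0.05: 1.991 × 1.342 = 2.67 joints
- alpha 0.02: 2.375 × 1.342 = 3.19 joints

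If the trial observed exactly its assumed result (difference 2.5, SD 6), then t = 1.86 and p = 0.066. That passes at 0.2 and fails at both levels in the SAP.

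**Sample size for 71% power**
- alpha 0.05: 74 evaluable per arm; 74/0.8 = 92.5, so 93 per arm, 186 enrolled
- alpha 0.02: 97 evaluable per arm; 97/0.8 = 121.25, so 122 per arm, 244 enrolled

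The plan is 100, or up to 170 after expansion.

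**The case against.** **The 0.02 is a slip.** Very likely. SAP 11 copies every other input and both powers from the protocol, those powers fit only 0.2, and no analysis section tests at 0.02. So 31%, 53% and 244 enrolled describe a test that probably nobody intends. This narrows the conflict to 0.2 against 0.05 but does not remove it.

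**SAP 6.1 is a default, and SAP 11 could be the exception it allows.** This is weak. SAP 11 justifies a sample size and sets no analysis rule, and read literally it would put the test at 0.02, where the stated power is furthest from true. Where the SAP wants a different level, for Part B, it says so in 6.5.

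**A t-test on completers is not the SAP's analysis.** This is fair. The primary analysis is a baseline-adjusted MMRM, it includes subjects with any post-baseline joint count, and it pools version 1 subjects who meet the joint criteria. The documents quantify no gain from any of these, so the following inputs are assumptions.
- Five extra version 1 subjects per arm (44 evaluable): 49% at 0.05 and 34% at 0.02.
- A baseline–outcome correlation of 0.4, with SD 6 taken as unadjusted: about 52% at 0.05.
- To reach 71% at 0.05 with 40 per arm, the effective SD would have to fall to about 4.4, a 46% cut in variance.

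Worst-observation imputation after treatment failure could also reduce the effect. The 45% is therefore an approximation, and a claim that the trial is more likely than not to miss its assumed effect at 0.05 is not robust, since modest gains bring power to about one half. The gap to 71% is robust.

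**Redaction.** SAP 3.2 is largely blacked out and the Appendix A1 list of analyses is not visible. An explanation there cannot be excluded, but it would not make 71% true at 0.02.

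**Part A is proof of concept.** The estimate, p-value and 95% interval will be reported whatever the threshold. That limits the harm to the success criterion and the power statement, but both are things the plan exists to fix.

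**Conclusion.** The concern holds. In the visible text the Part A primary test has no single significance level, and the SAP attaches 71% and 87% power to a level (0.02) at which the same inputs give about 31% and 53%. At the SAP's default of 0.05 they give about 45% and 67%. Only the protocol's two-sided 0.2 reproduces the stated powers, and the visible SAP nowhere sets that level.

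These figures rest on the documents' own SD, difference, sample size and dropout, with an unadjusted two-sample t-test and no version 1 subjects. The alternatives examined move power at 0.05 to between about 49% and 54% with 100 subjects, still well short of 71%. Treating 0.02 as a slip leaves the conflict between 0.2 and 0.05. This should be corrected before any unblinded Part A result is seen.

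**What to change.** State one two-sided level for the Part A primary comparison, identically in Protocol 16.8, SAP 6.1/6.2.1 and SAP 11, with power to match. Either route resolves it:

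- **(a) Keep the protocol's design level.** Correct 0.02 to 0.2 in SAP 11, and add to SAP 6.1 or 6.2.1 that the Part A primary test is at two-sided 0.20, as an exception to the 0.05 default. The 71% and 87% then stand. An 80% confidence interval beside the 95% interval would match the test but is optional.
- **(b) Keep 0.05.** Replace the alpha in Protocol 16.8 and SAP 11 and restate power as about 45% with 100 subjects and about 67% with 170. If the sponsor believes the MMRM or the pooled version 1 subjects raise this, the assumed gain should be stated.

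The cost is wording only: no extra subjects and no change to conduct. Route (a) openly accepts a 20% two-sided type I error for Part A. Route (b) makes the stated power less favourable.
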